## 9. CONCOMITANT MEDICATIONS

All concomitant medications (including herbal or alternative medicines) taken by the patient from the time of consent through the duration of protocol therapy will be recorded in the eCRF. Initiation of new systemic cGvHD therapy will be considered a new line of treatment and as study treatment failure.

Subsequent cGvHD therapies occurring during the follow up period (24 weeks) will also be captured.

### 9.1 Permitted concomitant medications

Patients may take their usual medications unless specifically prohibited by the Investigator team or listed as prohibited concomitant medications. Patients may receive red blood cell (RBC) or platelet transfusions, if clinically indicated, per local institutional guidelines.

### 9.2 Prohibited concomitant medications

Non-drug therapies with the intent of altering the immune response will not be permitted. Herbal or alternative medicines are also prohibited. Patients should not receive any form of chemotherapy, steroids (other than those initiated as first-line therapy and tapered off in the course of the trial) or COX2 inhibitors once beginning combination treatment.

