**Figure 1. Participant treatment schema**

## 3. OBJECTIVES

Primary Objectives	Primary Endpoints
To evaluate efficacy, tolerability and safety of combination treatment of belumosudil with ruxolitinib as second line therapy for steroid-refractory cGvHD.	
 
Efficacy will be assessed using overall response rate (ORR) as per the NIH cGvHD Consensus Response Criteria at 24 weeks of combination treatment (C8D1) of belumosudil with ruxolitinib (i.e., 28 weeks after C1D1).
 
Tolerability and safety will be assessed by the incidence and severity of adverse events (AEs) throughout the treatment duration using CTCAE v5.0 grading.
 

Secondary Objectives	Secondary Endpoints
To evaluate the response achievement with combination treatment of belumosudil with ruxolitinib as second line treatment for cGvHD.	
 
ORR as per the NIH cGvHD Consensus Response Criteria after 48 weeks of combination treatment of belumosudil with ruxolitinib (i.e., 52 weeks after C1D1).
 
Failure-free survival (FFS) after 24 and 48 weeks of combination treatment of belumosudil with ruxolitinib (i.e., 28 and 52 weeks after C1D1). FFS is defined as the time from treatment initiation until the occurrence of treatment failure.
 
Durable response rate in patients who achieve complete or partial response with combination treatment of belumosudil with ruxolitinib as assessed at 52 weeks from
 

	
C1D1. Durable response is defined as sustained improvement in symptoms or absence of disease progression from the time of treatment initiation.
 
4. Overall GvHD symptom burden improvement, serially measured with a modified Lee Symptom Scale (see Appendix D).

Exploratory Objectives	Exploratory Endpoints
To evaluate improvement in musculoskeletal involvement of sclerotic GvHD using the P-ROM score measurement.	1. Changes in the P-ROM score after 12, 24, and 48 weeks of combination therapy in patients who have developed sclerotic GvHD in musculoskeletal involvement of GvHD

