## 5. STUDY TREATMENT

### 5.1 Study Drug Administration

The Investigational Medicinal Product (IMP), Belmosudil, will be provided by Sanofi as 200 mg tablets.

Ruxolitinib will be dispensed as either 5 or 10 mg tablets, and will be obtained through the site's local pharmacy, as it will be administered per SOC.

All patients will receive open-label IMP. Responsibility for treatment of patients rests with the QI. Prior to initiating ruxolitinib (Cycle 1 Day 1), a tuberculosis skin test or interferon-gamma release assay should be performed in accordance with the approved JAKAVI® (ruxolitinib) product monograph to screen for latent tuberculosis infection, with results interpreted cautiously in immunocompromised patients. Positive results should prompt appropriate evaluation and management per institutional guidelines before starting isoniazid therapy. If the patient had been already treated with isoniazid prophylaxis for 6 months due to prior history of tuberculosis skin test or interferon-gamma release assay, this test will be exempted.

Eligible participants in this study will be started on ruxolitinib monotherapy orally at the standard recommended dose of 10 mg BID for 4 weeks (28 days). After one full cycle of ruxolitinib treatment (i.e., C2D1), the participant will have an AE assessment and, unless Grade  $\geq 3$  AE is observed, will continue on the same dose of ruxolitinib **plus** oral belumosudil 200 mg QD (or BID if receiving concomitant PPI) starting on C2D1.

In the event that the participant is experiencing Grade  $\geq 3$  AE(s) at the intended C2D1 visit assessment, treatment with belumosudil should not begin. This visit will be considered an unscheduled visit and the C2

D1 visit should be rescheduled. The participant can continue on ruxolitinib alone and should be followed for resolution of the Grade  $\geq 3$  AE(s). If the Grade  $\geq 3$  AE(s) improves to Grade  $\leq 2$  or resolves completely within 4 weeks, the participant will still be eligible to receive belumosudil. In this case, they should come back in for a true C2D1 visit and can complete all the necessary assessments as well as belumosudil dosing. If the Grade  $\geq 3$  AE(s) does not recover within 4 weeks, the participant will complete the End of Treatment visit and discontinue study. If there are any questions or concerns about the patient status and treatment in these scenarios, this should be discussed with the sponsor.

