### **7.2 Post-Baseline cGvHD Response Assessment**

The response assessment will be performed by the treating investigator according to the detailed schedule found in the study calendar. At each post-baseline visit, the response evaluation of each organ should be made by comparing the actual organ assessment versus the baseline status documented at C1D1. All organs that should be evaluated and

a high level summary of evaluation criteria as per NIH consensus guideline are listed in Table 6. Table 7 summarizes the rules for overall response assessment based on organ specific evaluation at each post-baseline visit.

**Table 6.** Organs included in cGVHD response assessment

Organ	Evaluation by	Criteria for response assessment
Skin	NIH Skin Score, considering %BSA involvement and sclerotic features	Change of skin score
Eyes	NIH Eye Score	Change of Eye score
Mouth	NIH Modified OMRS (Sum of scores for erythema, lichenoid and ulcers)	Change of OMRS
Esophagus	NIH Esophagus Score	Change of Esophagus score
Upper GI	NIH Upper GI Score	Change of Upper GI score
Lower GI	NIH Lower GI Score	Change of Lower GI score
Liver	Lab results for ALT, alkaline phosphatase, and Total bilirubin	Change of values for ALT, alkaline phosphatase, and Total bilirubin
Lungs	NIH Lung score AND %FEV1	Change of %FEV1
Joints and fascia	NIH Joint and Fascia Score and PROM scores	Change of Joint and Fascia Score and PROM scores

**Table 7.** Response determination for cGvHD based on all organs\*

Organ	Complete Response	Partial Response	Progression
Skin	NIH Skin Score 0 after previous involvement	Decrease in NIH Skin Score by 1 or more points	Increase in NIH Skin Score by 1 or more points, except 0 to 1
Eyes	NIH Eye Score 0 after previous involvement	Decrease in NIH Eye Score by 1 or more points	Increase in NIH Eye Score by 1 or more points, except 0 to 1
Mouth	NIH Modified Oral Mucosa Rating Score 0 after previous involvement	Decrease in NIH Modified Oral Mucosa Rating Score of 2 or more points	Increase in NIH Modified Oral Mucosa Rating Score of 2 or more points
Esophagus	NIH Esophagus Score 0 after previous involvement	Decrease in NIH Esophagus Score by 1 or more points	Increase in NIH Esophagus Score by 1 or more points, except 0 to 1
Upper GI	NIH Upper GI Score 0 after previous involvement	Decrease in NIH Upper GI Score by 1 or more points	Increase in NIH Upper GI Score by 1 or more points, except 0 to 1

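### A patient whose steroid dose is raised after C1D1 can count fully as a responder in the primary ORR, because Sections 9.2, 5.3 and 7.2 do not fit together on steroids

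*Protocol*

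**What the plan says.** All references are to the Protocol.

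- **Baseline.** Section 7.2 rates each organ by "comparing the actual organ assessment versus the baseline status documented at C1D1".
- **Readout.** Section 3 sets the primary ORR "at 24 weeks of combination treatment (C8D1) of belumosudil with ruxolitinib (i.e., 28 weeks after C1D1").
- **Lead-in.** Under Section 5.1 patients start with "ruxolitinib monotherapy orally at the standard recommended dose of 10 mg BID for 4 weeks (28 days"), and belumosudil joins at C2D1. If a Grade 3 or higher AE is present at the planned C2D1, that visit is deferred; if the event improves "or resolves completely within 4 weeks, the participant will still be eligible to receive belumosudil". The lead-in is therefore 4 weeks, and reaches 8 only in deferred cases.
- **Steroids at entry.** Sections 4.1 and 4.2 cap prednisone at 0.5 mg/kg/day at the time of enrollment. They set no limit afterwards.
- **Steroids on study.** The Section 9.2 restriction covers chemotherapy, "steroids (other than those initiated as first-line therapy and tapered off in the course of the trial") "or COX2 inhibitors once beginning combination treatment". It therefore applies from the start of combination treatment.
- **Directed increase.** Section 5.3 says the corticosteroid dose should be maintained or increased when ruxolitinib is interrupted abruptly for cytopenia. This is not tied to any cycle.
- **Failure rule.** Section 9: "Initiation of new systemic cGvHD therapy will be considered a new line of treatment and as study treatment failure".
- **Success rule.** Section 11.1 declares success with 37 or more responders out of 63, testing a null ORR of 49.7% against 66%. The null is based on ruxolitinib monotherapy.

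**The concern.** Response is change from C1D1, so anything that improves organ scores between C1D1 and C8D1 is credited to belumosudil plus ruxolitinib. A higher steroid dose is one such influence. From C1D1 to C2D1 no passage limits it. After C2D1 the first-line exemption still allows an existing steroid to continue, with no dose ceiling and no date by which the taper must be complete, and Section 5.3 can call for an increase.

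The trial has a single arm and is judged against a fixed rate, so no concurrent control absorbs the effect of a co-intervention. If steroid-assisted responses count, the chance of declaring success when belumosudil adds nothing goes up. It would also sit badly with the aim in Section 1.2 of reducing time on steroids.

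**Working it through.** **1. Can such a patient be counted as a responder?** Take a patient on a first-line steroid whose dose is raised above the C1D1 dose before C8D1 and who meets PR at C8D1.

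- Section 9 makes a new systemic cGvHD therapy a failure. A higher dose of the current steroid is not a new therapy.
- Section 5.6 lists the need for a medication the protocol does not allow, such as a new systemic agent, as a discretionary reason for removal. The first-line steroid falls within the Section 9.2 exemption.
- The failure definition in Section 11.3.1 needs progression or loss of response with a switch of systemic treatment, relapse, or non-relapse mortality. It serves FFS, not ORR.
- Tables 6 and 7 and the ORR paragraph of Section 11.3.1 do not mention steroid dose.

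Nothing removes this patient from the numerator. The path is open in the lead-in and also in Cycles 2 to 7.

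**2. The plan's success rule.** Inputs from Section 11.1: n = 63, cut-off 37, p0 = 0.497, p1 = 0.66. With X binomial:

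- P(X ≥ 37 | 63, 0.497) = 0.0953
- P(X ≥ 37 | 63, 0.66) = 0.910

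The rule behaves as a one-sided exact test at about 10% with 63 patients. Whether the 90% power stated for 57 patients holds is a separate matter and is not used here.

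**3. Sensitivity of the false-positive probability.** Let s be the share of patients whose steroid is raised and f the share of their would-be non-responses that become responses at week 28. Neither is in the documents; both are assumed. The ORR when belumosudil adds nothing becomes

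p = 0.497 + (1 − 0.497) × s × f = 0.497 + 0.503 × s × f

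| s | f | Shift 0.503·s·f | p | Expected extra responders (63 × shift) | P(X ≥ 37 of 63) |
|---|---|---|---|---|---|
| 0 | – | 0 | 0.4970 | 0 | 0.095 |
| 5% | 20% | 0.0050 | 0.5020 | 0.3 | 0.110 |
| 10% | 30% | 0.0151 | 0.5121 | 1.0 | 0.143 |
| 20% | 30% | 0.0302 | 0.5272 | 1.9 | 0.204 |

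The rule is sensitive to small shifts: one extra percentage point in the null ORR, from any source, gives 0.125. The table assumes that steroid increases contributed nothing to the reference rate and that escalated patients have the average non-response rate.

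**The case against.** **The effect may be very small.** Entry requires steroid-refractory disease, and one route is non-response to prednisone of at least 1 mg/kg/day. More of a drug that has failed would have to help, and the benefit would have to last to week 28. Patients who need an increase probably have worse disease than average. This stands and is why the low end is the more credible. It does not bring the effect to zero: another entry route is a dose increase after two failed tapers, where a higher dose could plausibly hold the disease.

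**The reference study may have had the same feature.** If steroid increases contributed equally to its 49% rate, the net bias could be near zero. The Protocol does not say how that study handled steroids, so this cannot be settled either way.

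**A steroid increase may already be a failure.** Section 2 lists a requirement for additional treatment among the FFS components. That wording does not name a dose increase, and it governs FFS rather than ORR.

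**The SAP could add a sensitivity analysis.** It could, and the absence of a table is not the fault here. A SAP cannot settle what Sections 9.2 and 5.3 allow or how they fit the C1D1 baseline.

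**Stronger readings the documents do not support.**

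- A reader might infer that the start date in Section 9.2 is the whole problem. It is not: the first-line exemption continues after C2D1, so moving the date alone would leave the gap open.
- A reader might extend the point to chemotherapy. That has little weight: relapse and planned maintenance therapy are excluded at entry, and new systemic cGvHD therapy is a failure under Section 9.
- A reader might take every patient to be affected, or the lead-in to be routinely 8 weeks. Only patients with an increase are affected, and 8 weeks needs a deferred C2D1.

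**Conclusion.** The gap is real on the text. A rise in an existing steroid above the C1D1 dose, at any time before C8D1, does not stop a patient from counting as a responder under the 37-of-63 rule. The cause is the combination of the Section 9.2 start date, its open-ended first-line exemption, the increase directed by Section 5.3 and the C1D1 baseline in Section 7.2.

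The size is uncertain and probably modest: about 1.5 percentage points on a 9.5% false-positive probability at the low end, and about 5 or 11 points under stronger assumptions. All of these rest on assumed escalation and conversion rates and on an unstated steroid policy in the reference study. None is an estimate of what will happen in this trial. The point is worth acting on because the comparison is with a fixed rate and the remedy is cheap.

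**What to change.** 1. Reconcile Section 9.2 (start of the restriction and first-line exemption), Section 5.3 (increase on abrupt ruxolitinib interruption) and Section 7.2 (C1D1 baseline). What is allowed clinically is for the clinical lead.
2. In Section 11.3.1, pre-specify that any patient whose systemic steroid dose rises above the C1D1 dose between C1D1 and C8D1 is flagged. A flag limited to the lead-in would miss the same increase nearer the readout.
3. Report the week-28 ORR with flagged patients kept in the denominator and counted as non-responders, beside the main ORR, and compare both with 37 of 63. State that a declared success is qualified if the two disagree. For example, 38 responders of whom 2 are flagged gives 36 and would be qualified.

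**Cost.** A few sentences and one extra analysis. Section 9 already has concomitant medications recorded from consent through protocol therapy.

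**Downside.** The second ORR is conservative, because some flagged patients would have responded anyway. If 5% were flagged and they responded at the design rate, the counted ORR would be 0.66 × 0.95 = 0.627, and P(X ≥ 37 of 63) would fall from 0.910 to 0.784. That is why it belongs beside the main ORR and not in its place.

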#### 9.2.1 Medications prohibited with belumosudil

The following medications are prohibited to be taken with belumosudil:

- Strong CYP3A inducers
- UGT1A1 substrates (e.g., raltegravir)
- P-gp substrates (e.g., dabigatran)
- OATP1B1/OATP1B3/BCRP substrates (e.g., rosuvastatin)

#### 9.2.2 Medication interactions with ruxolitinib

Please discuss all medication interactions with ruxolitinib with your care team, as per the standard of care treatment. However, the following interactions should be noted:

- Moderate CYP2C9 inhibitors (dose reduction recommended)
- Drugs that decrease heart rate/prolong PR interval (avoiding concomitant use is recommended)

### 9.3 Prevention of Pregnancy

Female patients of childbearing potential must use 2 reliable methods of birth control or be surgically sterile, or abstain from heterosexual activity (complete abstinence) for the

course of the study from study enrollment until 3 months following the last dose of any study therapy and agree not to donate or cryopreserve eggs (ova, oocytes) for the purpose of reproduction during this period. These patients must have a negative urine pregnancy test at screening, as well as a negative serum pregnancy on C1D1 prior to the administration of study intervention. The patient must be excluded from participation if the either pregnancy result is positive. Female patients of childbearing potential are those who have not been surgically sterilized (i.e. have a documented hysterectomy, or documented bilateral salpingectomy, or documented bilateral oophorectomy) or have not been free from menses for > 2 years. For individuals with permanent infertility due to an alternate medical cause other than the above (e.g. Mullerian agenesis, androgen insensitivity, gonadal dysgenesis) investigator discretion should be applied to determining study entry eligibility.

Male patients should agree to use a reliable method of contraception, or be surgically sterile, or abstain from heterosexual activity (complete abstinence), from study enrollment until 3 months following the last dose of any study therapy. These participants must refrain from donating or cryopreserving sperm, be abstinent from heterosexual intercourse as their preferred and usual lifestyle (abstinent on a long term and persistent basis) and agree to remain abstinent or must agree to use contraception (a male condom and an additional highly effective contraceptive method as described below) when having sexual intercourse with a woman of childbearing potential who is not currently pregnant.

Acceptable and reliable methods of contraception are:

- Condoms with contraceptive foam
- Oral, implantable or injectable contraceptives
- Contraceptive patch,
- Intrauterine device
- Intrauterine hormone-releasing system
- Diaphragm with spermicidal gel
- A sexual partner who is azoospermic (vasectomized or due to a medical cause), surgically sterilized or post-menopausal (in this instance, no additional contraception methods are required)

Complete abstinence is defined as complete avoidance of heterosexual intercourse during study treatment and for at least 1 month after completion of study treatment. Patients who choose complete abstinence are not required to use a second method of contraception. Acceptable alternate methods of effective contraception must be discussed in the event that the patient chooses to forego complete abstinence.

---

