	
11. Female patients of childbearing potential will use 2 reliable methods of birth control (refer to Section 9.3) or be surgically sterile, or abstain from heterosexual activity for the course of the study from the time of study enrollment until 3 months following the discontinuation of all study treatment and agree not to donate or cryopreserve eggs (ova, oocytes) for the purpose of reproduction during this period. Patients of childbearing potential are those who have not been surgically sterilized (i.e. have a documented hysterectomy, or documented bilateral salpingectomy, or documented bilateral oophorectomy) or have not been free from menses for > 2 years. For individuals with permanent infertility due to an alternate medical cause other than the above (e.g. Mullerian agenesis, androgen insensitivity, gonadal dysgenesis) investigator discretion should be applied to determining study entry eligibility.
 
Male patients will use an adequate method of contraception for the course of the study from the time of enrollment to 3 months after discontinuation of all study treatment. These participants must refrain from donating or cryopreserving sperm, be abstinent from heterosexual intercourse as their preferred and usual lifestyle (abstinent on a long term and persistent basis) and agree to remain abstinent or must agree to use contraception (a male condom and an additional highly effective contraceptive method as described in Section 9.3) when having sexual intercourse with a woman of childbearing potential who is not currently pregnant.
 
12. Patients showing overlap syndrome with components of aGvHD at the time of enrollment are eligible to participate unless the acute component of their overlap syndrome is Grade 3 or 4.
 
13. Must be able and willing to comply with study procedures.
 
Exclusion Criteria:
 
 
1. Have never been treated with systemic steroids as therapy for cGvHD.
 
2. Receiving >0.5 mg/kg/day of prednisone or equivalent corticosteroids at the time of enrollment.
 
3. Ongoing use of any of the following pharmaceutical agents, which cannot be discontinued prior to belumosudil treatment (PRN/as-needed use is permissible if it can be fully discontinued at least 7 days prior to enrollment and is not expected to resume during the study): 
 
• Strong CYP3A inducers
 
• UGT1A1 substrates (e.g., raltegravir)
 
• P-gp substrates (e.g., dabigatran)
 
 
 

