##### 4.1. Inclusion Criteria

1. For inclusion in this study, patients must fulfill all the following criteria: 18 years of age or older at the time of enrollment.
2. Has previously been diagnosed with moderate to severe cGvHD OR mild cGvHD with high-risk features (defined as platelet counts  $< 100 \times 10^9/L$  at screening).
3. Capable of providing informed consent.
4. Meets the criteria of steroid-refractory cGvHD after first line therapy at the time of enrollment, as follows:
  - Lack of response or disease progression after prednisone  $\geq 1$  mg/kg/day for  $\geq 1$  week **OR**
  - Disease persistence without improvement with prednisone  $> 0.5$  mg/kg/day or 1 mg/kg/every other day for  $\geq 4$  weeks **OR**
  - Increase in prednisone dose to  $> 0.25$  mg/kg/day after 2 unsuccessful attempts to taper the dose.
5. Taking a steroid dose at the time of enrollment that is  $\leq 0.5$  mg/kg/day of prednisone or equivalent

6. Absolute neutrophil count  $\geq 1.5 \times 10^9/\text{L}$  within 2 weeks (14 days) of enrollment.
7. Platelet count  $\geq 50 \times 10^9/\text{L}$  within 2 weeks of enrollment.
8. ALT and AST  $\leq 5 \times \text{ULN}$  ( $<7.5 \times \text{ULN}$  if due to liver GvHD) within 2 weeks of enrollment.
9. Total bilirubin  $\leq 1.5 \times \text{ULN}$  within 2 weeks of enrollment.
10. Glomerular filtration rate (GFR)  $\geq 30 \text{ mL/min/1.73 m}^2$  using the MDRD-4 variable formula within 2 weeks of enrollment.
11. Female patients of childbearing potential will use 2 reliable methods of birth control (refer to Section 9.3) or be surgically sterile, or abstain from heterosexual activity for the course of the study from the time of study enrollment until 3 months following the discontinuation of all study treatment and agree not to donate or cryopreserve eggs (ova, oocytes) for the purpose of reproduction during this period. Patients of childbearing potential are those who have not been surgically sterilized (i.e. have a documented hysterectomy, or documented bilateral salpingectomy, or documented bilateral oophorectomy) or have not been free from menses for  $> 2$  years. For individuals with permanent infertility due to an alternate medical cause other than the above (e.g. Mullerian agenesis, androgen insensitivity, gonadal dysgenesis) investigator discretion should be applied to determining study entry eligibility.  
  

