Male patients will use an adequate method of contraception for the course of the study from the time of enrollment to 3 months after discontinuation of all study treatment. These participants must refrain from donating or cryopreserving sperm, be abstinent from heterosexual intercourse as their preferred and usual lifestyle (abstinent on a long term and persistent basis) and agree to remain abstinent or must agree to use contraception (a male condom and an additional highly effective contraceptive method as described in Section 9.3) when having sexual intercourse with a woman of childbearing potential who is not currently pregnant.
12. The patients showing overlap syndrome with components of aGvHD at the time of enrollment can be enrolled unless their acute component of overlap syndrome is Grade 3 or 4 acute GvHD.
13. Must be able and willing to comply with study procedures.

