#### 5.4 Dose Tapering at End of Treatment/Discontinuation

Patients whose cGVHD has not progressed at the time of study treatment completion or discontinuation of combination treatment of belumosudil and ruxolitinib, for reasons other than AEs, should be tapered off belumosudil by reducing the dose every 2 weeks (14 days) as described below:

Starting dose of 200mg BID belumosudil → 200mg QD → 200mg QOD → Discontinue

---

---

**OR**

Starting dose of 200mg belumosudil QD → 200mg QOD → Discontinue

The belumosudil tapering process is to be initiated following the end of the 13 cycles of treatment (i.e., at EOT), and should last 4 weeks.

Tapering of ruxolitinib should be done slowly as per the product monograph, with documented CR or PR for at least 2 months, starting with a 50% dose reduction every 2 months (56 days). Initial dose reduction is to 5 mg orally BID. If sustained cGvHD response is observed (i.e. no worsening of cGvHD signs and symptoms), patient is further tapered by a second 50% dosage reduction to 5 mg orally QD for an additional 2 months (56 days), prior to cessation. The tapering process can be initiated prior to the EOT visit if the patient is responding well.

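### Section 9.3 defines complete abstinence with a 1-month minimum after treatment, while the same section and inclusion criterion 11 require 3 months

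*Protocol*

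**What the plan says.** The duty to prevent pregnancy appears in three places, each with a 3-month period after treatment.

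- **Section 9.3, opening paragraphs.** Women of childbearing potential must use contraception, be surgically sterile or practise complete abstinence for the "course of the study from study enrollment until 3 months following the last dose of any study therapy". Men should agree to contraception, sterility or to "abstain from heterosexual activity (complete abstinence), from study enrollment until 3 months following the last dose of any study therapy".
- **Section 4.1, inclusion criterion 11.** For women the period runs "until 3 months following the discontinuation of all study treatment". For men it runs "from the time of enrollment to 3 months after discontinuation of all study treatment".
- **Synopsis, inclusion criterion 11.** The period for women is again "from the time of study enrollment until 3 months following the discontinuation of all study treatment".

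The closing paragraph of section 9.3 then defines complete abstinence as avoidance of heterosexual intercourse "during study treatment and for at least 1 month after completion of study treatment". It adds that patients who choose this option need no second method, and that other effective methods must be discussed if the patient gives abstinence up.

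**The concern.** The definition carries its own duration, and that duration is shorter than the rule in which the term is used. It also runs from a different event: completion of study treatment, where the rule counts from the last dose of any study therapy. No text explains the difference by drug, sex or method.

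For a patient who relies on abstinence this is the only protection, because no second method is required, so its end date matters. The study calendar in section 8 schedules pregnancy tests only at screening and C1D1, so no later scheduled test would detect a pregnancy begun in the gap. A patient or site working from the definition alone could stop within the period for which the protocol requires pregnancy prevention.

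**Working it through.** The protocol gives no calculated figure to reproduce. The check sets the stated periods side by side and then works out the gap.

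**Periods compared**

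| Place | Starts | Ends |
|---|---|---|
| 9.3, rule for women | enrollment | 3 months after last dose of any study therapy |
| 9.3, rule for men | enrollment | 3 months after last dose of any study therapy |
| 4.1, criterion 11, both sexes | enrollment | 3 months after all study treatment is discontinued |
| 9.3, definition | during study treatment | at least 1 month after completion of study treatment |

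The difference at the start is minor, because treatment begins within 3 working days of enrollment (section 4.3). The difference at the end is the substance of the point.

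**Conversion.** 1 month = 365.25 / 12 = 30.4 days. 3 months = 3 × 365.25 / 12 = 91.3 days.

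**Case A: both periods start on the same day.** Shortfall = 91.3 − 30.4 = 60.9 days. This needs no interpretation.

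**Case B: completion is read as the End of Treatment visit.** This is an assumption. It has some support in section 5.4, which gives the taper instruction for "Patients whose cGVHD has not progressed at the time of study treatment completion or discontinuation of combination treatment of belumosudil and ruxolitinib" and says the belumosudil taper "is to be initiated following the end of the 13 cycles of treatment (i.e., at EOT), and should last 4 weeks". A footnote to section 8 uses the same term. On this reading the 1-month period starts before the last belumosudil dose and the 3-month period starts at that dose:

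shortfall = taper length + 91.3 − 30.4

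| Taper | Length | Shortfall | 1-month minimum ends after last belumosudil dose by |
|---|---|---|---|
| QD → QOD → stop, one 14-day step | 14 days | 14 + 91.3 − 30.4 = 74.9 days | 30.4 − 14 = 16.4 days |
| BID → QD → QOD → stop, two 14-day steps | 28 days | 28 + 91.3 − 30.4 = 88.9 days | 30.4 − 28 = 2.4 days |

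Section 5.4 is not uniform about taper length: a patient on 200 mg QD has one 14-day step, but the text says the taper should last 4 weeks. Both lengths are therefore shown. Ruxolitinib continued after week 52 as standard of care is not counted, because whether it is study therapy is equally open under the 3-month rule.

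**The case against.** The strongest reply is that the binding duty is clear and repeated. Section 9.3 opens with the 3 months, and criterion 11 makes it a condition of entry. The definition only sets a minimum, so 3 months of abstinence satisfies every text. Going wrong requires applying one sentence and ignoring the rest of its section. Patients act on the consent form and on site instructions, which are not available for this review.

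Much of this is fair, and it limits the likely harm. It does not make the definition correct: a stated minimum tells the reader when the obligation may end, and this one ends too early.

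There are also partial safeguards. Other methods must be discussed if abstinence is given up, although that does not correct the duration. Men must be abstinent as a long-term way of life and agree to remain so, or use a condom with a further highly effective method. The practical exposure therefore falls mainly on women of childbearing potential who choose abstinence.

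Finally, the 75- and 89-day figures depend on how completion is read, and the wording in section 5.4 belongs to a tapering instruction. The taper also applies only to patients without progression who stop for reasons other than adverse events. Those figures are illustrative. The 2-month gap does not depend on them.

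**Conclusion.** The point holds: the definition is wrong as written in an operative patient-safety rule. The explicit gap is 2 months, about 61 days. It rises to about 75 or 89 days only under the assumption that completion means the End of Treatment visit. How many of the at most 63 patients will rely on abstinence is not stated, so the harm is possible but cannot be quantified. The statistical design and the efficacy conclusions are unaffected. It should be corrected.

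**What to change.** Replace the defining sentence at the end of section 9.3 with one that uses the protocol's own period, for example: *Complete abstinence means no heterosexual intercourse from enrollment until 3 months after the last dose of any study therapy, including the belumosudil taper.* The duration and reference event are those already set in the opening paragraphs of section 9.3. Naming the taper is a clarification, since taper doses are doses of study therapy. The consent form should be checked for the same 1-month figure. The cost is one sentence in the protocol, with no change to design, sample size or analysis.
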